4.3.3 Study Period

The anticipated first patient in (FPI) is 1Q 2020 and the planned last patient last visit (LPLV) is 4Q 2020.

4.3.4 Study Termination

The end of study is defined as the date of the LPLV.

5. STUDY POPULATION

5.1 Inclusion Criteria

Patients will be eligible for study participation if they meet all of the following criteria:

- 1) Male or female, age 18 years or older on day of consent
- 2) Patients with routine unilateral cataract surgery on the day prior to study randomization
- 3) Patients with at least 5 cells in anterior chamber on the first day after surgery (at Visit 1)
- 4) Willing and able to understand and provide written ICF (at Visit -1)
- 5) Women who satisfy one of the following:
 - a) Are of child-bearing potential who are not pregnant or lactating and who are either abstinent or sexually active on an acceptable method of birth control (methods that can achieve a failure rate of less than 1% per year when used consistently and correctly, like hormonal contraception (oral pills, implantable device, or skin patch), intrauterine device, bilateral tubal occlusion, or double barrier) for at least 4 weeks prior to Visit 1 and throughout the study (i.e., until Day 29),

OR

b) Are post-menopausal (have had no menstrual cycle for at least one year prior to Visit -1) or have undergone a sterilization procedure (bilateral tubal ligation, hysterectomy, hysterectomy with unilateral or bilateral oophorectomy or bilateral oophorectomy) at least 6 months prior to Visit -1

5.2 Exclusion Criteria

The patients meeting any of the following criteria will not be permitted to enter the study:

- 1) Systemic administration of any corticosteroid or immunosuppressant drugs in the previous 2 weeks prior to the first instillation of the IMP
- 2) Periocular injection in the study eye of any corticosteroid solution within 4 weeks prior to the first instillation of the IMP, or of any corticosteroid depot within 2 months prior to the first instillation of the IMP (Ozurdex® [dexamethasone]: within prior 6 months; Iluvien® [fluocinolone]: within prior 36 months).
- 3) Instillation of any topical ocular corticosteroid, NSAID, mast cells stabilizers, antihistamines or decongestants within 2 weeks prior to the first instillation of the IMP, except pre-surgical and/or surgical administration of 1 drop of a topical NSAID or corticosteroid, at the investigator discretion
- 4) Prescription of any topical ocular medication, except preservative-free antibiotics for prophylactic purposes
- 5) Any history of glaucoma or ocular hypertension in the study eye
- 6) History or presence of endogenous uveitis
- 7) Any current corneal abrasion or ulceration
- 8) Any confirmed or suspected active viral, bacterial, or fungal keratoconjunctival disease
- 9) Known hypersensitivity or contraindication to the study drug or any of its components
- 10) History of steroid-related IOP increase

- 11) Previous surgery in the last 4 weeks prior to the Screening visit (Visit –1) or new surgery scheduled to be performed before the end of the study period on the contralateral eye
- 12) Presence of ocular hemorrhage which interferes with the evaluation of post-surgery inflammation
- 13) Presence of intraoperative complications during the cataract surgical procedure that may increase post-operative inflammation; this includes, in particular, patients with ocular hemorrhage, floppy iris syndrome, increased IOP (≥24 mmHg), posterior capsule rupture and injections of gas into the vitreous body
- 14) Increased cumulative dissipated energy value during phacoemulsification (increased energy used for phacoemulsification exert additional stress on iris and other anterior chamber structures and may generate excessive inflammation)
- 15) Presence of zonular dialysis (rupture of zonular fibers that attach lens to the ciliar body which may lead to partial luxation of the lens / lens capsule and is a serious complication of cataract surgery)
- 16) Presence of Fuchs´ endothelial dystrophy (loss of endothelial cells that may result in chronic corneal edema after cataract surgery especially if high energy was used during phacoemulsfication)
- 17) Presence of cornea guttata
- 18) Pupil dilation lower than 4.5 mm
- 19) Presence of lower lacrimal duct obstruction and/or history of infectious dacryocystitis
- 20) Presence of IOP ≥24 mmHg in the study eye at Visit 1
- 21) Participation in any study of an investigational topical or systemic new drug or device within 30 days prior to the Screening visit (Visit -1), or at any time during the study
- 22) Prior participation in the study described in this protocol, unless patient was not randomized
- 23) In the opinion of the investigator or study coordinator, be unwilling or unable to comply with study protocol or unable to successfully instill eye drops
- 24) Disease, condition (including monocular patients), or disorder that in the judgement of Investigator could confound study assessments or limit compliance to study protocol

5.2.1 Restrictions

Patients will be permitted to continue all their current ocular treatments, including the use of artificial tears, eyelid massage, or warm compresses, if they commit to using the same brand/regimen throughout the study.

None of the ocular treatments, whether over the counter (OTC) or prescription or study medication, should be used within 5 minutes of another ocular treatment during the study. Study medication should not be used within 30 minutes prior to any study visit.

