6.7.1 Prohibited Concomitant Medications

The use of the following medications is not permitted during the study:

- Any systemic or local therapy with corticosteroids (other than the study drug) or immunosuppressant (except pre-surgical and/or surgical administration of 1 drop of a topical NSAID or corticosteroid, at the investigator discretion)
- Any topical ocular medication (except preservative-free antibiotics for prophylactic purposes and preservative-free artificial tears).
- Any systemic NSAID or opioids drugs (except occasional use of OTC formulations titrated no more than one single dose per week)

The aforementioned medications will be considered as rescue medications when administered in patients not responding to the IMP (Section 6.7.2).

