Rescue medication shall be as reported as such in the eCRD. The following ATC3 codes of concomitant medication will be considered as prohibited medication if they are not classified as rescue medication (all medications will be reviewed and it will be considered whether any medication should be included or excluded in the prohibited classification):

- D07A Corticosteroids, plain
- D07B Corticosteroids, combinations with antiseptics
- D07C Corticosteroids, combinations with antibiotics
- D07X Corticosteroids, other combinations
- G01B Combinations of corticosteroids and antiinfectives for gynaecological use
- A01AC Corticosteroids for local oral treatment
- D01A Corticosteroids in combination with antifungals
- D10AA Corticosteroids, combinations for treatment of acne
- C05AA Antihemorrhoidals with corticosteroids
- S01B Antiinflammatory agents
- S02B Corticosteroids
- S02C Corticosteroids and antiinfectives in combination
- S03B Corticosteroids
- S03C Corticosteroids and antiinfectives in combination.
- H02 Corticosteroids for systemic use.
- L04A Immunosuppressants
- M01A Antiinflammatory and antirheumatic product, non-steroids
- N02BE NSAIDs in combination with paracetamol.
- M01B Salicylates in combination with corticosteroids.
- M01B Combinations of antiinflammatory/antirheumatic agents
- N02A Opioids
- Any ATC3 with ocular route except for S01A, S03A (Antiinfectives) preservative-free for prophylactic purposes and S01X (Other ophthalmologicals) preservative-free.

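### Protocol 5.2.1 lets patients keep ocular treatments, including preserved artificial tears, that 6.7.1 and the SAP prohibit, so using that permission can cost a patient a place in the per-protocol set.

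*Protocol*

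**What the plan says.** **Permission.** Protocol 5.2.1: "Patients will be permitted to continue all their current ocular treatments", with tears, warm compresses and lid massage given as examples, on condition that brand and regimen do not change. The section does not mention preservatives and does not refer to 6.7.1. Its spacing sentence reads "None of the ocular treatments, whether over the counter (OTC) or prescription or study medication, should be used within 5 minutes of another ocular treatment", so it envisages both kinds of product in use during the trial.

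**Entry.** Exclusion 4 in Protocol 5.2: "Prescription of any topical ocular medication, except preservative-free antibiotics for prophylactic purposes". It does not exempt tears, name an eye or give a time window.

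**Prohibition.** Protocol 6.7.1 forbids, during the study, "Any topical ocular medication (except preservative-free antibiotics for prophylactic purposes and preservative-free artificial tears"). It adds: "The aforementioned medications will be considered as rescue medications when administered in patients not responding to the IMP". SAP 6.3.1 repeats the list in its definition of rescue medication.

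**Coding.** SAP 6.3.9 treats as prohibited, if not already classified as rescue: "Any ATC3 with ocular route except for S01A, S03A (Antiinfectives) preservative-free for prophylactic purposes and S01X (Other ophthalmologicals) preservative-free". It also provides for a review of all medications that may move a product into or out of the prohibited class. No criterion is given and 5.2.1 is not mentioned.

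**Consequence.** Protocol 9.1.4 and SAP section 5 list entry-criteria violations and prohibited medication among the violations relevant to the PP set. For the primary and key secondary endpoints, the SAP's PP set requires no rescue or prohibited medication up to Visit 3. Protocol 10.4 names selection criteria and prohibited medication in its definition of a major deviation. SAP 6.2 assigns patients to analysis sets at a blinded review meeting.

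**The concern.** A rule that grants a permission and a rule that penalises its use cannot both stand. The PP analysis is the plan's stated robustness check for both main endpoints. It is meant to keep patients whose data show the treatment effect under intended use. Removing patients for something section 5.2.1 allowed works against that purpose, and who is removed would depend on which section a site followed.

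Protocol 4.1 allows no waivers except for immediate safety concerns, so sites have no documented way to settle the conflict locally. The masked review could settle it, but without a criterion two reasonable reviewers could classify the same preserved tear differently.

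**Working it through.** **1. The texts side by side**

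| Product in use at entry | 5.2.1 | Exclusion 4 | 6.7.1 and SAP 6.3.1 | SAP 6.3.9 | Conflict? |
|---|---|---|---|---|---|
| Eyelid massage, warm compresses | allowed | not a medication | not a medication | not coded | no |
| Preservative-free artificial tears, over the counter | allowed | not prescribed | exempt | exempt if coded S01X | no |
| Preservative-free artificial tears, prescribed | allowed | excluded at entry (tears not exempted) | exempt | exempt if coded S01X | yes, at entry |
| Preserved artificial tears, over the counter | allowed | not prescribed | prohibited | prohibited | yes |
| Other over-the-counter drops outside the classes in exclusion 3 | allowed | not prescribed | prohibited | prohibited unless preservative-free and in an exempt class | yes |
| Prescribed drops for the fellow eye | allowed | excluded if read as covering either eye | prohibited if read as covering either eye | prohibited outside the exempt classes | possibly |

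A preserved tear is flagged under SAP 6.3.9 however it is coded. If it falls in S01X, the exemption covers preservative-free products only. If it falls in another ocular-route class, the only other exemption is for preservative-free prophylactic anti-infectives.

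**2. Who remains after entry screening**

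Exclusion 3 removes recent users of topical steroids, NSAIDs, mast cell stabilizers, antihistamines and decongestants, apart from the single drop allowed around surgery. Exclusion 4 removes most prescribed topical ocular medication. Exclusion 5 removes study-eye glaucoma and ocular hypertension. The over-the-counter rows and possibly the fellow-eye row are left.

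**3. The plan's own sample size reproduces**

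Inputs from Protocol 9.1.1: p1 = 0.22, p0 = 0.07, allocation ratio r = 2, two-sided alpha 0.05, N = 202.

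- Odds ratio = (0.22/0.78)/(0.07/0.93) = 3.747, as stated.
- Pooled proportion = (2 × 0.22 + 0.07)/3 = 0.17.
- SD under the null = √[0.17 × 0.83 × 1.5] = 0.460. SD under the alternative = √[0.07 × 0.93 + 0.22 × 0.78/2] = 0.388.
- With n0 = 202/3 = 67.3, power = Φ[(0.15 × √67.3 − 1.96 × 0.460)/0.388] = 80.2%, against 80% stated.
- 202/0.96 = 210.4, against 210 stated.

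No stated figure is wrong.

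**4. Illustration of PP loss**

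The documents give no usage rate. Assume that 5-15% of the 210 randomized patients use an affected product, equally in both arms, that every one is excluded, that nobody else leaves the PP set, and that response rates are unchanged. Then 210 × 0.05 = 10.5 and 210 × 0.15 = 31.5 patients are lost.

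Exact power sums the binomial probabilities of all outcome pairs for which the uncorrected chi-square test rejects. The last column uses the formula in step 3.

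| Share lost | Active/placebo left | Exact power | Normal approximation |
|---|---|---|---|
| 0% | 140/70 | 83.4% | 81.8% |
| 5% | 133/67 | 81.9% | 79.6% |
| 10% | 126/63 | 79.7% | 77.1% |
| 15% | 119/60 | 76.5% | 74.5% |

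The two methods differ in level by about 2 points and fall by similar amounts. The textual conflict in step 1 does not depend on these numbers.

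**The case against.** The strongest reply has five parts.

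- **5.2.1 is a permission, not an obligation.** A reader might infer that sites cannot comply with both rules. They can: a site that applies exclusion 4 at entry and 6.7.1 afterwards breaches nothing in 5.2.1. This stands. The harm runs one way, to the patient who uses the permission.
- **Few products remain after screening.** This also stands. Exclusion 3 covers the topical steroids and NSAIDs of most concern for the primary endpoint, so the documents do not support a general claim that continued drops would distort cell counts. Over-the-counter preserved tears are still caught by none of exclusions 3 to 5, and 5.2.1 names tears as allowed.
- **6.7.1 could be read as supplying the qualifier that 5.2.1 omits, and the spacing sentence fits the products 6.7.1 exempts.** That reading is possible, but neither section refers to the other and 5.2.1 says all current treatments.
- **Removal from the PP set is not automatic.** SAP 6.2 and 6.3.9 provide a masked review. This stands, except that the review has no criterion and does not mention 5.2.1.
- **PP is supportive only.** This is correct. The FAS holds all randomized patients. A continued tear counts as rescue only if given for non-response, and SAP section 5 keeps users of prohibited medication in the FAS set without rescued patients.

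A reader might also infer bias between arms or uneven background treatment across sites. Treatment is masked and randomized, and the documents give no usage data, so neither is shown.

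**Conclusion.** The point holds as an internal inconsistency of limited reach. Preserved artificial tears, other over-the-counter drops and possibly fellow-eye drops are allowed by 5.2.1 and prohibited by 6.7.1 and the SAP. Exclusion 4 also disagrees with 6.7.1, because it does not exempt prescribed tears. Patients who use the permission are liable to leave the PP set for the primary and key secondary endpoints, subject to the masked review.

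The primary result in the FAS is not at risk from this unless a product is classed as rescue, in which case the patient counts as a treatment failure.

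The size is unknown. Under the assumed 5-15% usage with every user excluded, exact PP power falls from 83.4% to between 81.9% and 76.5%. The trial was not powered on the PP set, so these figures are illustrative and do not demonstrate a loss. The case for correction is that the PP set should not exclude patients for following the protocol.

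**What to change.** Reconcile Protocol 5.2.1, exclusion 4 in 5.2, Protocol 6.7.1, and SAP 6.3.1 and 6.3.9 so that one rule applies. The rule should say whether preservatives matter, which eye is meant, and whether tears are exempt at entry. Which rule prevails is for the sponsor.

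Carry the same rule into the PP definitions in Protocol 9.1.4 and SAP section 5. Give the masked review in SAP 6.2 and 6.3.9 a written criterion under which no patient leaves the PP set for a treatment the protocol permitted.

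The cost is a protocol clarification and matching SAP wording, with no change to sample size or data collection. The planned last visit was in 4Q 2020 and the SAP is dated 9 July 2021. If enrolment is over, the review criterion can still be fixed in writing, provided unmasking has not occurred. The report could then list the patients concerned and the decision taken for each.

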5.3 Withdrawal, Premature Discontinuation of Study Medication, and Replacement of Patients

Patients are free to discontinue their participation in the study at any time. Additionally, patients may be withdrawn from study at any time, if deemed necessary by the investigator

(after discussion with the Medical Monitor). Withdrawal from the study will not affect or prejudice the patients' further care or treatment.

Potential reasons for withdrawal of patients from this study are:

- The decision of a patient to withdraw informed consent
- Patient is lost to follow-up (Section 5.3.1)
- Potential reasons for premature discontinuation of study medication include, but are
 not limited to: Occurrence of a treatment-emergent AE (TEAE) or considerable
 worsening of an AE that, in the opinion of the investigator in consultation with the
 Medical Monitor and Sponsor, represents an unacceptable risk to the patient if he/she
 continues to receive study medication. The investigator must follow the patient until
 the AE resolves or satisfactorily stabilizes
- Administration of a rescue medication. Any patient placed on rescue therapy will discontinue the use of the IMP (see Sections 6.7.1 and 6.7.2)
- Patient's failure to comply with protocol requirements or study related procedures
- In case of pregnancy. The investigator will continue the follow-up of the patient until the end of the pregnancy
- Any surgery (different from the actual routine cataract surgery on the study eye) in the study or contralateral eye

In any case of premature discontinuation of study medication, the investigator must make extensive efforts to ensure that the patient will attend all his/her remaining study visits until study completion (at Visit 5), aiming to collect the most complete efficacy and safety data.

The reason and date the patient is withdrawn from the study will be documented in the eCRF (e.g. lost to follow-up, consent withdrawn, AEs, etc.).

If a patient is withdrawn from the study, the investigator should attempt to complete all discharge procedures (including the Early Termination Visit; Section 4.3.2.8). All AE s should be followed up according to Section 8.3.6.

If a patient is withdrawn from the study, or withdraw his/her consent, all data collected until the time of withdrawal will be used in the analyses, unless this is prohibited by local regulations.

Patients who drop out from the study will not be replaced.

5.3.1 Lost to Follow-up

A patient will be considered lost to follow-up if he/she fails to return for 2 consecutive scheduled visits and is unable to be contacted by the study center.

The following actions must be taken if a patient fails to return to the center for a required study visit:

 The center must attempt to contact the patient and reschedule the missed visit as soon as possible and counsel the patient on the importance of maintaining the assigned visit schedule and ascertain whether or not the participant wishes to and/or should continue in the study.

- Before a patient is deemed lost to follow up, the investigator or designee must make every effort to regain contact with the patient (where possible, 3 telephone calls and, if necessary, a certified letter to the patient's last known mailing address or local equivalent methods). These contact attempts should be documented in the patient's medical record.
- Should the patient continue to be unreachable, he/she will be considered to have withdrawn from the study with a primary reason of lost to follow-up.

5.3.2 Premature Termination of the Study

The investigator or the Sponsor may terminate this study prematurely for any reasonable cause. The Institutional Review Board (IRB) and Regulatory Authorities (RA) should be informed promptly.

Conditions that may warrant termination include, but are not limited to:

- The discovery of an unexpected, significant, or unacceptable risk to the patients enrolled in the study, or potential study patients
- A decision on the part of the Sponsor to suspend or discontinue development of clobetasol propionate ophthalmic nanoemulsion 0.05%
- The Sponsor decides to discontinue the study

If the RA obtains information that raises doubts about the safety or scientific validity of the clinical study, the RA can suspend or prohibit the study.

If the study is prematurely terminated or suspended for any reason, the investigator/institution should promptly inform the study patients and should assure appropriate therapy and follow-up for the patients.

5.4 Planned Sample Size

The study will be conducted in approximately 20 centers in the US. Approximately a 15% of screening failures is expected. At least 210 patients will be randomized (140 to clobetasol arm, 70 to placebo arm, in a 2:1 randomization ratio) in order to have 202 evaluable patients (4% lost to follow-up rate expected).

A rationale of the calculation of sample size is provided in Section 9.1.1.

Patient selection will be based on the inclusion and exclusion criteria. Patients who meet each of the inclusion criteria at the Screening Visit and/or Baseline Visit (as applicable) and none of the exclusion criteria at the Screening Visit and/or Baseline Visit (as applicable) are eligible to be randomized in this study. A patient could be re-screened only after the Sponsor's approval.

5.5 Patient Identification and Randomization

Patients will be randomized at Visit 1, (24 h after cataract surgery) after eligibility criteria revaluation. Randomization will be conducted through an Interactive Web Response System (IWRS) include blocking. The IWRS will assign a patient number, which will be used to identify the patient during screening and, if applicable, throughout the duration of the study. Patients who do not meet the eligibility criteria will be registered as screen failures through the IWRS.

6. STUDY MEDICATION

6.1 Identity

Investigational Medication

Generic name Clobetasol propionate ophthalmic nanoemulsion 0.05

%

Trade name Not applicable

Dosage form Ophthalmic nanoemulsion, sterile

Manufacturer SALVAT

Description Ophthalmic nanoemulsion in single-dose low-density

polyethylene (LDPE) translucent vials containing 0.17

mL deliverable volume

Reference Medication

Generic name Vehicle

Trade name Not applicable

Dosage form Ophthalmic nanoemulsion, sterile

Manufacturer SALVAT

Description Ophthalmic nanoemulsion in single-dose low-density

polyethylene (LDPE) translucent vials containing 0.17

mL deliverable volume

Clobetasol propionate ophthalmic nanoemulsion 0.05% is an oil-in-water (o/w) nanoemulsion containing the active ingredient clobetasol propionate at a concentration of 0.05% weight per weight (w/w). The compendial name as per the European Pharmacopoeia is clobetasol propionate.

Clobetasol propionate ophthalmic nanoemulsion 0.05% is a clear solution or slightly yellowish nanoemulsion at a concentration of 0.05%.

Placebo (vehicle) is identical in appearance and composition to clobetasol propionate ophthalmic nanoemulsion 0.05% but without the active substance.

Inactive ingredients in the IMPs are polysorbate 80, medium chain triglycerides, benzalkonium chloride, ethylenediaminetetraacetic acid (EDTA), povidone, tris(hydroxymethyl)aminomethane hydrochloride, tris(hydroxymethyl)aminomethane, glycerin and water for injection.

